4.5.8 Diagnostic Renal Biopsy

For determination of study eligibility, the local biopsy report will be used. Where possible, the renal biopsy used for eligibility determination will be sent to a central specialist review laboratory before being returned to the study site. This central reading is not used to determine study eligibility. Micrographs may be transferred, if available, in lieu of tissue where transfer of tissue is not possible (e.g., not allowed per local regulation or insufficient sample).

4.5.9 Optional Renal Biopsy

Patients will be offered an optional renal biopsy following the Week 76 assessment and may undergo additional biopsies at any other time if deemed clinically appropriate by the investigator. This optional assessment may provide histologic evidence of disease activity or remission beyond the laboratory response measurements.

The Informed Consent Form will contain a separate section that addresses optional biopsies. A separate, specific signature will be required to document a patient's agreement to undergo optional biopsies. The investigator should document whether or not the patient has given consent to participate and (if applicable) the date(s) of consent, by completing the Sample Informed Consent/Withdrawal eCRF.

Samples may be used for exploratory biomarker research as described in Section 4.5.5. For sampling procedures, storage conditions, and shipment instructions, see the laboratory manual. Refer to Section 4.5.5 for details on duration of sample storage, use of samples after patient withdrawal, confidentiality standards for data, and availability of data from biomarker analyses.

4.5.10 Optional Samples for Research Biosample Repository 4.5.10.1 Overview of the Research Biosample Repository

The Research Biosample Repository (RBR) is a centrally administered group of facilities used for the long-term storage of human biological specimens, including body fluids, solid tissues, and derivatives thereof (e.g., DNA, RNA, proteins, peptides). The collection, storage, and analysis of RBR samples will facilitate the rational design of new pharmaceutical agents and the development of diagnostic tests, which may allow for individualized drug therapy for patients in the future.

Samples for the RBR will be collected from patients who give specific consent to participate in this optional research. RBR samples will be analyzed to achieve one or more of the following objectives:

- To study the association of biomarkers with efficacy or disease progression
- To identify safety biomarkers that are associated with susceptibility to developing adverse events or can lead to improved adverse event monitoring or investigation
- To increase knowledge and understanding of disease biology and drug safety
- To study drug response, including drug effects and the processes of drug absorption and disposition
- To develop biomarker or diagnostic assays and establish the performance characteristics of these assays

4.5.10.2 Approval by the Institutional Review Board or Ethics Committee

Collection, storage, and analysis of RBR samples is contingent upon the review and approval of the exploratory research and the RBR portion of the Informed Consent Form by each site's Institutional Review Board or Ethics Committee (IRB/EC) and, if applicable, an appropriate regulatory body. If a site has not been granted approval for RBR sampling, this section of the protocol (Section 4.5.10) will not be applicable at that site.

4.5.10.3 Sample Collection

The following samples will be stored in the RBR and used for research purposes, including, but not limited to, research on biomarkers related to obinutuzumab, diseases, or drug safety:

- Blood samples collected at the baseline (Day 1) visit and/or subsequent visits
- Leftover blood, serum, plasma, urine, and renal tissue samples (with the exception
 of remaining archival tissue blocks, which will be returned to sites) and any
 derivatives thereof (e.g., DNA, RNA, proteins, peptides), including leftover tissue
 samples from medically indicated procedures (e.g., kidney biopsy) performed at the
 investigator's discretion during the course of the study

The above samples may be sent to one or more laboratories for analysis of germline or somatic variants via whole genome sequencing (WGS), whole exome sequencing (WES), or other genomic analysis methods. Genomics is increasingly informing researcher's understanding of disease pathobiology. WGS and WES provide a comprehensive characterization of the genome and exome, respectively, and, along with clinical data collected in this study, may increase the opportunity for developing new therapeutic approaches or new methods for monitoring efficacy and safety or predicting which patients are more likely to respond to a drug or develop adverse events.

Data generated from RBR samples will be analyzed in the context of this study but may also be explored in aggregate with data from other studies. The availability of a larger

dataset will assist in identification and characterization of important biomarkers and pathways to support future drug development.

For sampling procedures, storage conditions, and shipment instructions, see the laboratory manual.

RBR samples are to be stored until they are no longer needed or until they are exhausted. However, the RBR storage period will be in accordance with the IRB/EC-approved Informed Consent Form and applicable laws (e.g., health authority requirements).

4.5.10.4 Confidentiality

RBR samples and associated data will be labeled with a unique patient identification number.

Patient medical information associated with RBR samples is confidential and may be disclosed to third parties only as permitted by the Informed Consent Form (or separate authorization for use and disclosure of personal health information) signed by the patient, unless permitted or required by law.

Given the complexity and exploratory nature of the analyses of RBR samples, data derived from these analyses will generally not be provided to study investigators or patients unless required by law. The aggregate results of any conducted research will be available in accordance with the effective Sponsor policy on study data publication.

Data generated from RBR samples must be available for inspection upon request by representatives of national and local health authorities, and Sponsor monitors, representatives, and collaborators, as appropriate.

Any inventions and resulting patents, improvements, and/or know-how originating from the use of the RBR data will become and remain the exclusive and unburdened property of the Sponsor, except where agreed otherwise.

4.5.10.5 Consent to Participate in the optional Research Biosample Repository

The Informed Consent Form will contain a separate section that addresses optional participation in the RBR. The investigator or authorized designee will explain to each patient the objectives, methods, and potential hazards of participation in the RBR. Patients will be told that they are free to refuse to participate and may withdraw their consent at any time and for any reason during the storage period. A separate, specific signature will be required to document a patient's agreement to provide optional RBR samples. Patients who decline to participate will not provide a separate signature.

The investigator should document whether or not the patient has given consent to participate and (if applicable) the date(s) of consent, by completing the Sample Informed Consent/Withdrawal eCRF.

In the event of an RBR participant's death or loss of competence, the participant's samples and data will continue to be used as part of the RBR research.

4.5.10.6 Withdrawal from the Research Biosample Repository

Patients who give consent to provide RBR samples have the right to withdraw their consent at any time for any reason. After withdrawal of consent, any remaining samples will be destroyed. However, if RBR samples have been tested prior to withdrawal of consent, results from those tests will remain as part of the overall research data. If a patient wishes to withdraw consent to the testing of his or her RBR samples during the study, the investigator must inform the Medical Monitor in writing of the patient's wishes through use of the appropriate RBR Subject Withdrawal Form and must enter the date of withdrawal on the Sample Informed Consent/Withdrawal eCRF. If a patient wishes to withdraw consent to the testing of his or her RBR samples after closure of the site, the investigator must inform the Sponsor by emailing the study number and patient number to the following email address:

[contact]

A patient's withdrawal from this study does not, by itself, constitute withdrawal of consent for testing of RBR samples. Likewise, a patient's withdrawal of consent for testing of RBR samples does not constitute withdrawal from this study.

4.5.10.7 Monitoring and Oversight

RBR samples will be tracked in a manner consistent with Good Clinical Practice by a quality-controlled, auditable, and appropriately validated laboratory information management system, to ensure compliance with data confidentiality as well as adherence to authorized use of samples as specified in this protocol and in the Informed Consent Form. Sponsor monitors and auditors will have direct access to appropriate parts of records relating to patient participation in the RBR for the purposes of verifying the data provided to the Sponsor. The site will permit monitoring, audits, IRB/EC review, and health authority inspections by providing direct access to source data and documents related to the RBR samples.

4.6 UNPLANNED VISITS

Unplanned visits may be performed if clinically indicated. Adverse events, concomitant medications, and vital signs must be assessed for each unplanned visit. Other procedures, tests, and assessments will be performed at the discretion of the investigator.

Patients who develop new or worsening lupus symptoms or for whom a flare is suspected should be seen at the investigational site, as soon as possible, regardless of

the dates of their scheduled study visits or the study period. SLEDAI-2K, urinalysis, including UPCR, chemistry panel, and additional procedures (see Appendix 1 schedule of activities) should be performed by the examining investigator (or their designee, as applicable) at all unplanned visits related to a suspected disease flare. For definition of renal and extrarenal flares, as well as, protocol guidance on corticosteroid dosing see Appendix 5. For reporting disease flares, see Section 5.3.5.10.

4.7 TREATMENT, PATIENT, STUDY, AND SITE DISCONTINUATION

4.7.1 Study Treatment Discontinuation

Patients must permanently discontinue obinutuzumab or placebo infusions if they experience any of the following:

- Any medical condition that the investigator or Sponsor determines may jeopardize the patient's safety if study treatment is continued
- Investigator or Sponsor determination that treatment discontinuation is in the best interest of the patient
- Pregnancy
- Grade 4 IRR or recurrence of Grade 3 IRR upon re-challenge
- Grade 3 or 4 neutropenia that does not resolve to Grade ≤2 within 8 weeks
- Grade 3 or 4 thrombocytopenia (not due to SLE) that does not resolve to Grade ≤2 within 8 weeks
- Hepatitis B reactivation despite the initiation of the appropriate anti-viral therapy
- Receipt of rescue therapy as defined in Section 4.4.4.1

The primary reason for study treatment discontinuation should be documented on the appropriate eCRF. Patients who discontinue study treatment prematurely will not be replaced. Any patient who discontinues treatment should continue to undergo protocol-mandated visits.

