4.3.1 Study Treatment Dosage, Administration, and Compliance

The treatment regimens are summarized in Sections 3.1.2 and 3.1.3.

Refer to the pharmacy manual for detailed instructions on drug preparation, storage, and administration.

Any dose modification should be noted on the Study Drug Administration electronic Case Report Form (eCRF). Cases of overdose, medication error, drug abuse, or drug misuse, along with any associated adverse events, should be reported as described in Section 5.3.5.12.

Guidelines for treatment interruption or discontinuation, and for resumption, for patients who experience adverse events are provided in Section 5.1.3.

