5.1.3.2 Treatment Interruption

Obinutuzumab/placebo infusions may be slowed or withheld for patients who experience toxicity considered to be related to study drug (see Section 5.1.3.3).

In addition, prior to resuming either obinutuzumab/placebo study drug treatment:

- Any infection experienced at any time during the study must have fully resolved.
- ANC levels and platelet counts at the last blood sample analysis must not meet the study treatment discontinuation criteria (see Section 4.7.1).
- The patient must not have developed any of the following:
 - Active infection of any kind, excluding fungal infection of the nail beds
 - Significant or uncontrolled medical disease which, in the investigator's opinion, would preclude patient participation
- The patient must not be pregnant.

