Infections: Hepatitis B	 Hepatitis B screening is required prior to initiation of obinutuzumab or placebo infusions. Patients with active or chronic hepatitis B (surface Ag+) will be excluded from the study. Patients who are core antibody positive (HBcAb+) with no detectable DNA will be allowed into the study but require monthly HBV DNA monitoring until 12 months after the last dose of obinutuzumab or placebo. Anti-viral therapy should be considered. If HBV reactivation (as defined in the most recent version of the obinutuzumab autoimmune Investigator's Brochure) is observed: Obinutuzumab or placebo infusions should be permanently discontinued (see Section 4.7.1). Reduction or interruption of MMF should be considered, per local guidelines. Antiviral therapy must be started as per EASL 2017 Clinical Practice guidelines or local guidelines. Referral to a hepatologist is recommended. Patients will be monitored regularly for transaminitis. If transaminitis is observed, patients will be promptly referred to a hepatologist for evaluation and treatment.
Suspected PML	 Stop obinutuzumab or placebo infusions and MMF. Obtain neurological consult. In consultation with a neurologist, we recommend obtaining an MRI and performing a lumbar puncture to assess for CSF JC viral DNA. Notify monitors immediately.
Neutropenia	 Patients who experience neutropenia should be closely monitored with regular laboratory tests until resolution. MMF dose should be adjusted as per guidance in Appendix 7. If treatment is necessary, it should be administered in accordance with local guidelines and administration of granulocyte colony stimulating factors should be considered. Any signs of concomitant infection should be treated as appropriate. Grade 3 or 4 neutropenia that does not resolve to Grade ≤2 within 8 weeks is a treatment-discontinuation criterion. Cases of late onset neutropenia (occurring ≥ 28 days after the end of treatment) or prolonged neutropenia (lasting more than 28 days after treatment has been completed/stopped) have also been reported in studies of obinutuzumab for hematologic malignancy.

CSF=cerebrospinal fluid; GI=gastrointestinal; HBcAb=hepatitis B core antibody; HBV=hepatitis B virus; IRR=infusion-related reaction; IVIG=intravenous immunoglobulin; JC=John Cunningham; MMF=mycophenolate mofetil; MRI=magnetic resonance imaging; PML=progressive multifocal leukoencephalopathy.

Table 5 Guidelines for Management of Specific Adverse Events (cont.)

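### Protocol 4.7.1 requires stopping for hepatitis B reactivation only despite anti-viral therapy, but Table 5 calls for a permanent stop on any reactivation and cites 4.7.1 for it

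*Protocol*

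**What the plan says.** Section 4.7.1 of the protocol opens its list with "Patients must permanently discontinue obinutuzumab or placebo infusions if they experience any of the following". The one item on hepatitis B reads "Hepatitis B reactivation despite the initiation of the appropriate anti-viral therapy". The list also has two general grounds that rest on judgment: a condition that the investigator or Sponsor considers a danger to the patient, and the patient's best interest.

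The hepatitis B row of Table 5 (Section 5.1.3.3) covers two stages.

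- **Before any reactivation.** Patients positive for hepatitis B core antibody (HBcAb) with no detectable HBV DNA may enrol and need monthly HBV DNA monitoring. On prophylaxis the row says only "Anti-viral therapy should be considered".
- **Once reactivation, as defined in the Investigator's Brochure, is observed.** The row gives "Obinutuzumab or placebo infusions should be permanently discontinued (see Section 4.7.1" and, as a separate action, "Antiviral therapy must be started as per EASL 2017 Clinical Practice guidelines or local guidelines".

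Two other places bear on how a site would act. Section 4.3.1 says "Guidelines for treatment interruption or discontinuation, and for resumption, for patients who experience adverse events are provided in Section 5.1.3". Section 5.1.3.2, on interruption, begins "Obinutuzumab/placebo infusions may be slowed or withheld for patients who experience toxicity considered to be related to study drug (see Section 5.1.3.3" and then sets conditions for resuming, among them "Any infection experienced at any time during the study must have fully resolved". Those conditions refer to 4.7.1 for neutrophil and platelet counts but do not name hepatitis B.

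**The concern.** The section written as the mandatory list carries the less protective rule, and the section with the more protective rule points to that list as its reference. The verbs run the same way: the narrow trigger has *must* and the broad one has *should*. By naming a specific hepatitis B trigger, 4.7.1 also implies that a reactivation that responds to treatment is not a mandatory stop.

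Section 5.1.1.2 says that HBV reactivation with anti-CD20 antibodies, including obinutuzumab in hematologic malignancies, can end in fulminant hepatitis, hepatic failure and death. HBcAb-positive patients without detectable HBV DNA are eligible (Section 4.1.2). Infusions can continue every 6 months after Week 76 (Sections 3.1.2 and 3.1.3), so the question of restarting could arise over a long period.

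**Working it through.** The plan states no figure on this point, so the check is mainly a comparison of texts.

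**Step 1: what each trigger requires.** Table 5 needs one thing, reactivation by the Investigator's Brochure definition. The 4.7.1 item needs reactivation and, in addition, that it happens despite anti-viral therapy having been started.

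**Step 2: the two readings of *despite*.** It could mean reactivation while on prophylaxis, or reactivation that persists after treatment has begun.

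| Patient | 4.7.1 hepatitis B item | Table 5 |
|---|---|---|
| Not on anti-virals, first reactivation just observed | Not met on either reading | Permanent stop |
| Same patient, anti-virals started, responds | Not met on either reading | Permanent stop |
| Reactivates while on prophylaxis | Met on the first reading | Permanent stop |
| Reactivation persists on treatment | Met on the second reading | Permanent stop (already due at observation) |

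The first two rows are where the texts part. They are not far-fetched, because prophylaxis is only to be considered.

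**Step 3: does the cross-reference hold?** Section 4.7.1 is not silent on hepatitis B, but it does not contain the unconditional rule. Its general grounds could lead to a stop, but by judgment, not automatically on observed reactivation. The neutropenia row of Table 5, by contrast, repeats the 4.7.1 neutropenia criterion.

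**Step 4: resumption.** The conditions in 5.1.3.2 are necessary ones and do not by themselves authorise a restart. But none of them rules out a restart after hepatitis B reactivation, and the protocol does not say what full resolution means for this infection.

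**Step 5: how many patients.** The documents give neither a reactivation rate nor an HBcAb-positive count for this trial. Section 5.1.1.2 reports no cases in the Phase II study (NOBILITY) through Week 104, after four scheduled infusions (Section 1.3). The size of its obinutuzumab arm can be inferred:

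- 10 patients reported as 16% (Section 5.1.1.1) and 2 patients as 3.2% (Section 5.1.1.9) leave n = 62 or 63.
- The 6.3% serious-infection rate (Section 5.1.1.2) fits 4/63 = 6.35%. No whole number out of 62 gives it (4/62 = 6.45%). So n = 63.
- As a consistency check, 3/63 = 4.76% agrees with the 4.8% reported for Grade 3 or higher infections.

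With 0 events in n patients, the one-sided 95% upper limit is 1 − 0.05^(1/n). For n = 63 this is 1 − 0.05^(1/63) = 4.64%.

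This limit covers any reactivation among all treated Phase II patients. It is not a maximum. It says nothing specific about HBcAb-positive patients, and it does not measure how often a site would restart.

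**The case against.** The strongest reply is that no instruction in the protocol is contradicted. Section 4.7.1 does not claim to be complete and never permits continuing after a first reactivation. Other permanent stops also sit outside its specific items, for example confirmed PML (Section 5.1.1.2) and suspected hypersensitivity during infusion (Table 5). Section 4.3.1 sends sites to Section 5.1.3, and 5.1.3.2 cites 5.1.3.3 in its first sentence, so a restart means overlooking Table 5. The protocol also uses *should* for the PML stop, which nobody would read as optional. There are further safeguards: monthly HBV DNA monitoring, reporting of any reactivation within 24 hours as an event of special interest (Sections 5.2.3 and 5.4), and the Section 4.5 rule that dosing goes ahead only if clinical and laboratory findings are acceptable.

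Much of this stands. A site following both texts would stop, 5.1.3.2 does not grant permission to resume, and the verb alone proves little. It keeps the issue minor but does not remove it. The PML row in Table 5 does not cite 4.7.1, and 4.7.1 has no specific PML item. For hepatitis B, 4.7.1 states its own, narrower trigger, and Table 5 cites 4.7.1 beside a broader one. The cross-reference might be meant only to point to the discontinuation procedures, but a reader who follows it still meets a different hepatitis B criterion.

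It is also fair to say that the Phase II limit gives no number of affected patients, and that how often the two triggers would diverge depends on a definition in the Investigator's Brochure, which is not among the documents.

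**Conclusion.** The inconsistency is real on either reading of *despite*. Section 4.7.1 should not stand as written, because the mandatory list gives a less protective hepatitis B rule than the table that cites it.

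It is minor. The texts can be followed together, safeguards exist, and few patients are likely to be affected. The rate in HBcAb-positive patients and the chance of a restart cannot be derived from the documents. The 4.6% limit is background only and rests on the inferred Phase II arm size of 63.

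There is no meaningful effect on the primary analysis. Treatment discontinuation is handled by treatment policy (Protocol 6.3.1, SAP 4.2.1), and patients who stop infusions continue their visits.

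**What to change.** Replace the hepatitis B item in 4.7.1 with reactivation as defined in the current Investigator's Brochure, without the anti-viral condition. It then matches Table 5, and the cross-reference becomes correct. Optionally, add a line to 5.1.3.2 saying that infusions are not to be resumed after HBV reactivation. Tell the sites.

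The text change is one item and one optional line, plus a site letter. Because it alters a stopping rule, it also needs the ordinary amendment route in Section 9.7: ethics approval and, where locally required, regulatory approval. It could be carried in the next amendment. Data collection and analysis do not change.
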